### **6.4. Demographics and Background Characteristics**

Subject demographics including sex, birth date, race, and whether the subject has child-bearing potential will be collected in CRF. Information on HLH history including pHLH diagnosis, genetic test result (molecular diagnosis), NK-cell functional test result, family history, and conventional treatment received will be collected in details via CRF. Medical history including name of the medical condition or event, start and end date, and ongoing status will be collected in CRF. Medical history data will be coded using the latest updated English version of Medical Dictionary for Regulatory Activities (MedDRA).

Analysis on demographic data and background characteristics will be based on all treated subjects. Subjects' demographic and background characteristics will be summarized using descriptive statistics. And data listings will be provided. For conventional treatment record, pHLH conventional treatment history including medication and non-drug therapy will be

presented. Prior pHLH conventional medication will be tabulated by anatomical main group and therapeutic subgroup, and prior pHLH conventional non-drug therapy will be tabulated by therapy name. A medication/non-drug therapy will be considered pHLH conventional medication/non-drug therapy if the indication is conventional pHLH treatment (ongoing or discontinued at screening) as reflected in the CRF. A pHLH conventional medication/therapy will be considered treatment history if the start date is earlier than the date of first infusion. For records with its start date completely or partially missing, similar method as described in [Section 6.2.1 will be applied \(replacing end date by start date in the specified rules\)](#). For medical history data, concurrent disease and condition will be tabulated separately from medical history record and historic event. A medical history record with its ongoing status specified as yes will be considered concurrent (and otherwise historic event). Medical history and concurrent disease will be tabulated at subject level grouping by System Organ Classes (SOCs) and Preferred Terms (PTs).

Analysis of safety assessments at screening visit will be based on all treated subjects, for other details please refer to [Section 6.10](#).

## **6.5. Exposure and Compliance**

IMP administration including level of dose prescribed, prescribed dose, date, time and duration of dose administration, and information on dose increase and dose interruption will be collected in the CRF.

The total prescribed dose, total dose administered, total duration of dosing (in days), and average dose frequency (times per day) will be summarized using descriptive statistics. The dose administered will be calculated based on prescribed dose and approximate proportion administered (refer to [Section 6.2.2](#)). The total duration of dosing will be calculated based on the date of last infusion and the date of first infusion (refer to [Section 6.2.2](#)). The average dosing frequency will be calculated based on the total duration of dosing and the total number of records of emapalumab infusion (refer to [Section 6.2.2](#)).

The emapalumab dose change from the first dosing will be summarized showing the number and percentage of patients with a dose increase or a dose decrease at each visit. Moreover, the percentage of dose increases and decreases from the first dose for each patient will be summarized using a descriptive table. Percentage of dose increase or decrease from first dose will be calculated based on prescribed dose at first dosing and prescribed dose at each visit (refer to [Section 6.2.2](#)).

Data listing containing all information collected for IMP administration will be provided. In addition, IMP administration will be listed at patient level including all dose adjustments over time and summarized in terms of the number of doses administered, maximum dose, equivalent dose of dexamethasone, duration of exposure from the first dose to the last dose of treatment, cumulative dose, average dose frequency and average dose per day.

## **6.6. Prior/Concomitant Medication and Non-Drug Therapy**

Medication name, dosage, frequency, route, start and end date, indication and ongoing status will be collected for prior/concomitant medication in the CRF. For non-drug therapy, information including therapy name, start and end date, indication and ongoing status will be collected.

Prior and concomitant medications will be coded using the latest updated global version of World Health Organization Drug Dictionary (WHO-DD) B3 format. A medication/therapy will be considered concomitant if the end date is equal to or later than the date of first infusion, and will be considered as prior medication/therapy otherwise. For records with its end date completely or partially missing, please refer to [Section 6.2.1](#).

The frequency and percentage of prior and concomitant medications will be tabulated at subject level grouping by anatomical main group, therapeutic subgroup, chemical subgroup and generic name. The frequency and percentage of prior and concomitant non-drug therapy will be tabulated at subject level grouping by therapy name.

In addition, concomitant pHLH conventional medication will be tabulated by anatomical main group and therapeutic subgroup, and concomitant pHLH conventional non-drug therapy will be tabulated by therapy name.

## **6.7. Primary Analysis**

Primary analysis on permanent discontinuation of study drug due to emapalumab-related adverse events will be based on all treated analysis set.

### **6.7.1. Primary Estimand Analysis**

#### Permanent Discontinuation of Study Drug Due to Emapalumab-Related AEs

The treatment policy strategy will be applied for estimating the primary endpoint. Permanent discontinuation of study drug due to emapalumab-related adverse events will be estimated as described below regardless of any potential intercurrent events.

The number and percentage of subjects who permanently discontinue study drug due to emapalumab-related AEs will be presented.

## **6.8. Secondary Analysis**

All secondary analyses will be based on all treated analysis set unless specified otherwise.

### **6.8.1. Secondary Analysis Supporting Primary Objective**

For the definition and determination of treatment-emergent AEs/SAEs, refer to [Section 6.10.2](#).

#### Treatment-Emergent AEs

The treatment policy strategy will be applied for estimating the incidence of treatment-emergent AEs. AEs recorded since receiving the first dose of investigational medication until EOS will be presented regardless of any potential intercurrent events.

The overall incidence of treatment-emergent AEs will be summarized at event level and subject level by SOCs and PTs.

#### Treatment-Emergent SAEs

The treatment policy strategy will be applied for estimating the incidence of treatment-emergent SAEs. SAEs recorded since receiving the first dose of investigational medication until EOS will be presented regardless of any potential intercurrent events.

The overall incidence of treatment-emergent SAEs will be summarized at event level and subject level by SOCs and PTs.

### Treatment-Emergent Laboratory Abnormalities

The treatment policy strategy will be applied for estimating the incidence of treatment-emergent laboratory abnormalities. Laboratory abnormalities recorded since receiving the first dose of investigational medication until EOS will be presented regardless of any potential intercurrent events. Laboratory abnormalities that are absent at baseline will be considered treatment-emergent.

The overall incidence of treatment-emergent laboratory abnormalities will be summarized at event level and subject level by test name (e.g. hematology, biochemistry, coagulation, sCD25, urinalysis, or cerebrospinal fluid analysis if applicable) and test item.

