### 3. Estimand

Objectives	Endpoints	Estimand
Primary Objective: To collect safety data on emapalumab in treatment-experienced Chinese pHLH patients	Primary Endpoint: Permanent discontinuation of study drug due to emapalumab-related adverse events as judged by the investigator	Estimand 1: Primary Estimand Target population: All patients received at least one infusion of IMP Treatment: Refer to Section 6.4 in study protocol Endpoints: Refer to the left column Strategies for addressing intercurrent events: The treatment policy strategy will be applied for the estimand Population-level summary: The number and percentage of patients who permanently discontinue study drug due to emapalumab-related adverse events
	Secondary Endpoint 1: Treatment-emergent adverse events (AEs)	Estimand 1.1 Target population: All patients received at least one infusion of IMP Treatment: Refer to Section 6.4 in study protocol Endpoints: Refer to the left column Strategies for addressing intercurrent events: The treatment policy strategy will be applied for the estimand Population-level summary: Incidence of treatment-emergent AEs
	Secondary Endpoint 2: Treatment-emergent serious adverse events (SAEs)	Estimand 1.2 Target population: All patients received at least one infusion of IMP Treatment: Refer to Section 6.4 in study protocol Endpoints: Refer to the left column Strategies for addressing intercurrent events: The treatment policy strategy will be applied for the estimand Population-level summary: Incidence of treatment-emergent SAEs (refer to Section 6.8)
	Secondary Endpoint 3:	Estimand 1.3

	
Treatment-emergent laboratory abnormalities
	
Target population: All patients received at least one infusion of IMP          Treatment: Refer to Section 6.4 in study protocol          Endpoints: Refer to the left column          Strategies for addressing intercurrent events:          The treatment policy strategy will be applied for the estimand          Population-level summary:          Incidence of treatment-emergent laboratory abnormalities (refer to Section 6.8)

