	
Secondary Endpoint 4:          Treatment-emergent vital sign abnormalities
	
Estimand 1.4          Target population: All patients received at least one infusion of IMP          Treatment: Refer to Section 6.4 in study protocol          Endpoints: Refer to the left column          Strategies for addressing intercurrent events:          The treatment policy strategy will be applied for the estimand          Population-level summary:          Incidence of treatment-emergent vital sign abnormalities (refer to Section 6.8)

Secondary Objective:          To collect efficacy data on emapalumab in treatment-experienced Chinese pHLH patients
	
Secondary Endpoint 1:          Overall Response, i.e., achievement of either Complete or Partial Response or HLH Improvement, at EOT or Week 8 (whichever occurs earlier)
	
Estimand 2.1          Target population: All patients received at least one infusion of IMP          Treatment: Refer to Section 6.4 in study protocol          Endpoints: Refer to the left column          Strategies for addressing intercurrent events:          The treatment policy strategy will be applied for the estimand          Population-level summary:          The number and percentage of patients achieving overall response and each component of overall response at EOT or week 8 (whichever occurs earlier)

	
Secondary Endpoint 2:          Time to first Overall Response, i.e., time from the date of first dose of
	
Estimand 2.2          Target population: All patients received at least one infusion of IMP

[figure not shown]
	
emapalumab to the first achievement of response (Complete or Partial Response or HLH Improvement)
	
Treatment: Refer to Section 6.4 in study protocol          Endpoints: Refer to the left column          Strategies for addressing intercurrent events:          The treatment policy strategy will be applied for the estimand          Population-level summary:          Time to first response prior to HSCT will be estimated using Kaplan-Meier method

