### Treatment-Emergent Vital Sign Abnormalities

The treatment policy strategy will be applied for estimating the incidence of treatment-emergent vital sign abnormalities. Vital sign abnormalities recorded since receiving the first dose of investigational medication until EOS will be presented regardless of any potential intercurrent events. Vital sign abnormalities that are absent at baseline will be considered treatment-emergent.

The overall incidence of treatment-emergent vital sign abnormalities will be summarized at event level and subject level by test item.

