## **6.8.2. Secondary Analysis Supporting Secondary Objectives**

### Overall Response

Achievement of response will be assessed after the database lock via a programmed algorithm. The derivation of the Overall Response is detailed below.

Overall Response		
Response	Definition	Additional Clarifications
Complete Response	Complete Response is adjudicated if: 
 
- No fever = body temperature <37.5°C
 
- Normal spleen size
 
- No cytopenia = Absolute Neutrophil Counts <math>\geq 1.0 \times 10^9/L</math> and platelet count <math>\geq 100 \times 10^9/L</math> [absence of G-CSF and transfusion support must be documented for at least 4 days to report no cytopenia]
 
- No hyperferritinemia = serum ferritin level is <2000 <math>\mu g/L</math>
 
- No evidence of coagulopathy, i.e., normal D-Dimer and/or normal (>150 mg/dL) fibrinogen levels
 
- No neurological and CSF abnormalities attributed to HLH
 
- No sustained worsening of sCD25 (as indicated by at least two consecutive measurements that are > 2-fold higher than baseline)
 
	
 
- All HLH parameters that were abnormal at baseline must be normalized
 
- No AEs relating to organ failure
 
- All other parameters that were normal at baseline must still meet the definition of normalized
 
- Normal spleen size confirmed by abdominal ultrasound (US) whenever possible based on the splenomegaly not present; if US not performed physical examination will be used
 
- Normal D-Dimer levels are <math>\leq 500 \mu g/L</math>
 
- No neurological abnormalities attributed to HLH = “normal” neurological assessment by investigator in the neurological examination page (without findings in brain imaging (Brain MRI/Brain CT/cranial ultrasound) or AEs indicative of “CNS involvement”
 
- No CSF abnormalities = no AE indicative of “CSF abnormalities”
 

Partial Response	Partial Response is adjudicated if: 
 
- At least 3 of the HLH clinical and laboratory abnormalities (including CNS abnormalities) meet
 
	If a patient is not considered as “reactivated” or a patient is considered “reactivated” with 4 or more abnormal HLH features upon entry to the study and

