### **6.10.2. Laboratory Test Results**

Data on the test item(s), result, clinical significance, unit, normal range limits, and additional comments for hematology, biochemistry, coagulation, sCD25, urinalysis, and cerebrospinal fluid (CSF) analysis (if clinically indicated) will be documented in the CRF. Laboratory test data will be collected at all scheduled visits for the treatment period and the follow-up period.

The numeric findings of laboratory test result (including hematology, biochemistry, coagulation, sCD25, CSF analysis, and urinalysis) will be summarized for screening visit and following visits using descriptive statistics. Actual values and actual changes from baseline will be presented. Qualitative clinical evaluation (normal, not clinically significant, clinically significant, or not done) will be tabulated for screening visit and presented using shift table for following visits. CSF analysis will only be tabulated for subjects with available baseline CSF analysis results and available CSF results for at least one post-treatment visit.

Listings will be provided for all laboratory data collected for scheduled and unscheduled visits. In addition, all abnormal laboratory findings of subjects with normal result at baseline will be listed.

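### The laboratory and vital-sign incidence tables in SAP 6.8.1 have no route for worsening from an abnormal baseline and do not show how many patients could be counted

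*SAP*

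**What the plan says.** SAP 6.8.1 gives one criterion for each endpoint. For laboratory items: "Laboratory abnormalities that are absent at baseline will be considered treatment-emergent". For vital signs: "Vital sign abnormalities that are absent at baseline will be considered treatment-emergent". Both tables run from first dose to end of study and summarise events and subjects. Neither paragraph defines an abnormality, sets a grade or threshold, or mentions worsening. Protocol 8.3.3.1 names the endpoints without defining treatment-emergent, so it does not fill the gap.

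In SAP section 3, Estimands 1.3 and 1.4 take all treated patients as the target population and incidence as the summary. SAP 6.8 confirms the set: "All secondary analyses will be based on all treated analysis set unless specified otherwise".

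Elsewhere, SAP 6.10.2 collects a clinical category for each laboratory result: "Qualitative clinical evaluation (normal, not clinically significant, clinically significant, or not done) will be tabulated for screening visit", with shift tables for later visits. It also plans a separate listing in which "all abnormal laboratory findings of subjects with normal result at baseline will be listed". SAP 6.10.4 treats vital signs in the same way.

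**The concern.** These are two of the four secondary endpoints supporting the primary safety objective. Protocol 6.3.1 requires active HLH at entry, and the SAP's response algorithm expects abnormal starting values ("All HLH parameters that were abnormal at baseline must be normalized"). The rule therefore fits least well on the items the disease itself disturbs.

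On such an item the denominator is every treated patient, but the numerator can draw only on those without the abnormality at baseline. A low figure could mean that few patients deteriorated or that few were countable, and the table does not show which. The adverse-event rules of the same study differ: Protocol 6.5.5.1.1 makes a pre-existing condition reportable when it worsens.

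The undefined term is a second problem. Absence at baseline could be judged per item, per direction (low or high) or per clinical category, and two programmers could produce different tables.

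**Working it through.** The documents give no figure on this point, so there is none to reproduce. The check has four steps.

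**1. Is there any other route to treatment-emergent status?**
- SAP 6.8.1: the abnormality was not there at baseline. Nothing else is stated.
- SAP section 3 refers back to 6.8.
- SAP 6.1 defines baseline as the last value before first dose and adds no worsening rule.
- SAP 6.10.2 and 6.10.4 plan summaries, shift tables and listings. They do not redefine the term.
- Protocol 8.3.3.1 gives no definition.

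That the stated criterion is the sole one is an inference, but no other is given.

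**2. What does this do to a subject-level incidence?** Let n be the treated patients and k those already abnormal on an item. Reading abnormal against normal, the highest incidence that can be reported is (n − k)/n. Planned n is 10 to 18. The values of k below are assumptions.

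| n | k | Maximum incidence |
|---|---|---|
| 18 | 4 | 14/18 = 77.8% |
| 18 | 9 | 9/18 = 50.0% |
| 18 | 14 | 4/18 = 22.2% |
| 18 | 16 | 2/18 = 11.1% |
| 10 | 2 | 8/10 = 80% |
| 10 | 5 | 5/10 = 50% |
| 10 | 8 | 2/10 = 20% |
| 10 | 9 | 1/10 = 10% |

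Each further patient abnormal at baseline costs 1/18 = 5.6 points or 1/10 = 10 points. For items rarely abnormal at entry, k is near zero and little changes.

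**3. Is k likely to be above zero?** Of the eight HLH-2004 criteria in Protocol 6.3.1, three lie outside these tables: splenomegaly, hemophagocytosis and NK-cell activity. A patient who qualifies on five must have met at least 5 − 3 = 2 of those inside (fever, cytopenias, triglycerides/fibrinogen, ferritin, sCD25). This supports expecting some abnormal baselines but fixes k for no single item. The criteria may have been met before baseline, and patients can instead enter on molecular diagnosis or family history.

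**4. What would counting category worsening change?** If a move to a worse clinical category counts, only patients already clinically significant at baseline (c of them, c ≤ k) stay uncountable for that item and direction, and the maximum becomes (n − c)/n. For example, assuming n = 18, k = 9 and c = 4, it rises from 50.0% to 14/18 = 77.8%.

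**The case against.** The strongest reply is that the information is largely available elsewhere. Clinically significant laboratory values and vital signs are to be reported as adverse events (Protocol 6.5.7 and 6.5.6.1), worsening pre-existing conditions are reportable (6.5.5.1.1), and treatment-emergent adverse events are themselves an endpoint under the same objective. SAP 6.10.2 and 6.10.4 add change from baseline, shift tables and full listings. The study is small and descriptive, with no hypothesis tests. The affected items are mainly disease markers whose course the response algorithm follows, so a new-onset rule for a safety table can be defended.

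Much of this stands. A reader might infer that worsening disappears from the safety analysis; the documents do not support that. What remains is that by-visit shift tables do not give per-patient incidence over the study, which is what Estimands 1.3 and 1.4 name, and the adverse-event route depends mainly on the investigator's judgement of clinical significance.

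The objection is also right that the ceiling depends on one reading. If absence is judged by direction or by clinical category, a low-to-high change or a move from not clinically significant to clinically significant could already count as new. The normal-at-baseline listings do not settle this, since they are additional outputs in another section. Nor does the ceiling cap event-level counts.

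Finally, a numeric rule for worsening of values already clinically significant would need item- and direction-specific limits. Setting these now, in an open-label study whose SAP reached version 4.0 in August 2025, risks choosing them with data in view. That is a good reason not to add one.

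**Conclusion.** The point holds in a limited form. As written, the rule gives no route for worsening from an abnormal baseline in two secondary safety tables whose denominator is all treated patients, and it leaves the key term undefined. On the normal-versus-abnormal reading, a low incidence for a disease-affected item cannot be interpreted from the table alone.

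The size is unknown. The ceilings above rest on assumed baseline counts and on that reading. A reader might infer that incidence will be understated by a calculable amount; without baseline shares and rates of worsening, the documents do not support that. The primary endpoint, discontinuation for drug-related adverse events, is not affected. This is a low-cost improvement in clarity and completeness and does not show that a safety signal would be missed.

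**What to change.** In SAP 6.8.1:

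1. State that an abnormality is judged per test item and, where applicable, per direction (low or high). Count it as treatment-emergent if it is new or if the post-baseline category is worse than the baseline category, using the categories already collected: normal, not clinically significant, clinically significant.
2. Show new and worsened counts in separate columns. Beside each item, print how many patients were in each of the three categories at baseline, so that the number at risk is visible.
3. Add no numeric threshold for values already clinically significant at baseline. Instead, footnote the table to say that worsening within that category is not counted there, and refer to the adverse-event tables and change-from-baseline summaries.

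As a separate and optional addition, present both tables prior to and after HSCT alongside the full-period table, as SAP 6.10.1 already plans for adverse events.

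The cost is SAP wording and a little programming, with no new data. Some of the added events will reflect HLH activity rather than drug effect; the separate columns keep that visible and preserve the new-onset count.
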